8. RESEARCH QUESTION AND OBJECTIVES

To compare the early intervention effectiveness of Tio/Olo vs. Tio among COPD patients.

The primary objective of this study is to:

- Compare time to LAMA/LABA/ICS triple therapy initiation among initiators of Tio/Olo vs. initiators of Tio.

The secondary objectives of the study are to compare the following among initiators of Tio/Olo vs. initiators of Tio:

Secondary outcomes

- Time to First Moderate or Severe COPD Exacerbation
 - Time to First Moderate COPD Exacerbation
 - Time to First Severe COPD Exacerbation
- Number of Moderate or Severe COPD Exacerbations
 - Number of Moderate COPD Exacerbations
 - Number of Severe COPD Exacerbations

Further endpoints:

- All-Cause Mortality,
- Number of Unique Pulmonary Medication Prescriptions
- Number of Hospitalizations for a Respiratory Condition
- Major Cardiovascular Adverse Events (MACE)
- Home oxygen therapy (HOT)

9. RESEARCH METHODS

9.1 STUDY DESIGN

This will be a new-user, active comparator retrospective comparative cohort study using MDV Japan, a Japanese electronic healthcare research database. It will employ high dimensional propensity scores (hdPS) to match 1 Tiotropium initiator for each Tiotropium/Olodaterol initiator.

9.2 SETTING

9.2.1 Definitions

Study Period: the entire period of time that includes the baseline period, the cohort entry date (index date), and follow-up period for the study population. The study period will be from **01 April 2015** (180 days prior to Spiolto approval date of 28 September 2015 in Japan) to **31 March 2019** (end of available data).

Patient Selection Period: the period of time for which patients are eligible to enter the cohort. The earliest date of the patient selection period is **28 September 2015**, (the Spiolto approval date in Japan). The latest date of the patient selection period is 31 December 2018, corresponding to 90 days before the end of available data (31 March 2019), ensuring that all patients have at least 60 days after the cohort entry date to identify a second prescription for index therapy and at least 30 days to be capable of the 30-day overlap to determine the triple therapy initiation outcome.

Cohort Entry Date: Date of entry to the initial cohort of Tio/Olo vs. Tio users (*first prescription*).

Baseline Period: the 180-day period that ends 1 day prior to the cohort entry date used to assess covariate information. The earliest start of the baseline period would be 01 April 2015, corresponding to 180 days prior to the approval date of Spiolto.

[figure not shown]
Follow-Up Period: the period starting at the second prescription for Tio/Olo or Tio within 60 days of the cohort entry date (first prescription) and ending at the earliest occurrence of the outcome (use of triple therapy), or the first occurrence of inpatient death, disenrollment, or end of the study period (31-Mar-2019). A sensitivity analysis will employ an as-treated censoring approach to further censor upon discontinuation of index therapy or initiation of the other index treatment arm. Patients may have different lengths of follow-up (i.e. variable follow-up).

Since health care is nationalized in Japan, the notion of enrollment is not applicable. Therefore, a proxy enrolment criterion defined as start of enrolment = date of first inpatient/outpatient encounter; end of enrolment = date of last inpatient/outpatient encounter will be used. “Enrolment” herein will refer to this proxy enrolment measure. For entry into the study population, patients will be required to have had at least 180 days of enrollment prior to the cohort entry date.

Data during the baseline period will be used to confirm study eligibility and classification of exposure. The follow-up period will be used for identifying the outcome. This is illustrated in [Figure 1](#).

Figure 1

Study timeline

*Patients are allowed to enter the cohort between 28-September-2015 and 31-December-2018. The last allowable date for start of follow-up is 1-March-2019. The follow-up ends at the earliest occurrence of the outcome, or the first occurrence of inpatient death, disenrollment, or end of the study period (31-Mar-2019). A sensitivity analysis will employ an as-treated censoring approach to further censor upon discontinuation of index therapy or initiation of the other index treatment arm.

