9.3.2 Outcomes

9.3.2.1 Primary outcomes

Triple Therapy Use

[figure not shown]
The primary outcome of interest is incident rate of triple therapy initiation (first event per patient) defined as any LAMA/LABA/ICS fixed dose combination or any concurrent use for 30 consecutive days of the following:

- any LAMA/LABA fixed dose combination + any ICS single formulation
- any LAMA single formulation + any LABA/ICS fixed dose combination
- any LAMA single formulation + any LABA single formulation + any ICS single formulation

MDV data has limited information on treatment duration with the days of prescription recorded as 1 day for most patients. Therefore, a days supply of 30 days will be assumed. Although we will require at least 30 days of overlap, the first date of triple therapy overlap will serve as the outcome event date, as corresponds to the initiation of triple therapy. Looking into the future to satisfy the requirement of overlap for at least 30 days has the potential to inflict immortal person-time, but is necessary to differentiate concurrent use when subsequent medication is added (see [Figure 3](#) - example Patient A) from an early sequential prescription fill when subsequent medication is switched to (see [Figure 3](#) - example Patient B).

Figure 3

Illustration of outcome

Censoring

Patients will be censored if they had an occurrence of any of the following: outcome (initiation of triple therapy), death, or end of data. The analysis will use an intention-to-treat censoring approach, which does not account for treatment change. A sensitivity analysis will employ an as-treated censoring approach to further censor upon discontinuation of index therapy or initiation of the other index treatment arm. Thus, events will be assigned to exposure groups according to that patient's original index medication, even if that patient discontinued or crossed over.

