9.3.2.2 Secondary outcomes and further endpoints

Secondary outcomes

- Time to First Moderate or Severe COPD Exacerbation
 - Time to First Moderate COPD Exacerbation
 - Time to First Severe COPD Exacerbation
- Number of Moderate or Severe COPD Exacerbations
 - Number of Moderate COPD Exacerbations
 - Number of Severe COPD Exacerbations

Further endpoints:

- All-Cause Inpatient Mortality
- Number of Unique Pulmonary Medications
- Number of Hospitalizations for a Respiratory Condition
- Major Cardiovascular Adverse Events (MACE)
- Home oxygen therapy (HOT)

Moderate exacerbations will be defined as an outpatient visit with a diagnosis code for COPD in any field + a prescription for an oral corticosteroid or an antibiotic for respiratory infections,. Severe

exacerbations will be defined as a hospitalization with a primary diagnosis for COPD. (**Chatterjee 2012**)

Unique pulmonary medications will be defined as the following treatments: LAMA, LABA, SAMA, SABA, inhaled/oral glucocorticoids, systemic glucocorticoids, antileukotriene agents, biologics (anti-IgE, anti-IL-5, anti-IL-4), allergy medications, xanthines (theophylline), and mycolytics.

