9.7.3 Sensitivity Analyses

1. Less Stringent Qualifying Event Criterion

Instead of defining the event to qualify patients for inclusion based on two prescriptions within 60 days, patients may enter upon only one prescription. While some confidence is lost in whether the patients truly took their index medications, the less stringent qualifying event criterion will allow more patients to be included, increasing statistical power. Furthermore, the possibility of immortal time bias is also mitigated, since the time between prescriptions is no longer present.

2. As-treated Censoring

The analysis will use an as-treated approach for primary, secondary and further endpoint outcomes. In addition to the censoring criteria mentioned for the intention-to-treat approach (outcome, death, or end of data), patients will also be censored after medication discontinuation or switching over to the other arm.

3. Alternative algorithm for COPD

The analysis will use a different set of diagnosis codes for COPD (J43*, J44*) when selecting COPD patients. Compared to the primary analysis, this algorithm omits the diagnostic code for chronic bronchitis (J41*), as this code is commonly used by pulmonologists when prescribing Mucodyne to patients who do not actually have chronic bronchitis. While some true chronic bronchitis patients may be excluded, the selection of patient will increase specificity.

4. Asthma patients with doubt

Asthma patients with doubt are defined as patients with a diagnosis code for asthma and without evidence of any asthma specific treatment (ie., ICS, ICS/LABA). This sensitivity analysis will include patients identified with asthma with doubt.

5. ACOS sensitivity analysis

Patients that have evidence of asthma during the follow-up period will have their data censored on the date of asthma diagnosis during the follow-up period. This will ensure that they contribute information during their COPD disease trajectory up until the time they develop asthma. This approach will mitigate introducing immortal time bias for those patients with ACOS during the follow-up period.

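### The plan's only follow-up period ends at triple therapy, so events after escalation drop out of the secondary and further endpoints

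*Combined protocol and SAP*

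**What the plan says.** The Follow-Up Period in 9.2.1 starts at the second index prescription, "ending at the earliest occurrence of the outcome (use of triple therapy), or the first occurrence of inpatient death". The other ends it allows are proxy disenrolment and 31 March 2019. The note to Figure 1 repeats the rule with the outcome in the singular and unnamed: "The follow-up ends at the earliest occurrence of the outcome, or the first occurrence of inpatient death, disenrollment, or end of the study period". The Censoring paragraph of 9.3.2.1 names it again: "Patients will be censored if they had an occurrence of any of the following: outcome (initiation of triple therapy), death, or end of data". The same paragraph adds: "The analysis will use an intention-to-treat censoring approach, which does not account for treatment change".

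Section 9.3.2.2 lists time to first exacerbation, "Number of Moderate or Severe COPD Exacerbations", inpatient mortality, unique pulmonary medications, respiratory hospitalisations, MACE and home oxygen. It gives none of them a follow-up end. The as-treated analysis in 9.7.3 covers every endpoint: "The analysis will use an as-treated approach for primary, secondary and further endpoint outcomes". It builds on the main list: "In addition to the censoring criteria mentioned for the intention-to-treat approach (outcome, death, or end of data"). The rates, risks and Cox model in 9.7.1 concern triple therapy only, so nothing later in the plan supplies a different window.

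**The concern.** The secondary objective in Section 8 compares initiators of Tio/Olo with initiators of Tio. A programmer who follows 9.2.1 literally would stop observing each patient at escalation. The result would then describe outcomes before triple therapy, not outcomes after starting the index drug.

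Two features make this more than lost precision. Section 7 says that uncontrolled, exacerbating patients are the ones who may escalate, and it uses escalation as a proxy for worsening. Patients would therefore tend to leave follow-up when their risk is high. Escalation is also the primary outcome and is expected to differ between arms, so the amount removed would differ too. Ending follow-up at an escalation of treatment also sits uneasily with an intention-to-treat approach that is meant to disregard treatment change.

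**Working it through.** **Inputs.** From 9.5: triple therapy within 1 year in 6% (Tio/Olo) and 10% (Tio), and 1,829 Tio/Olo new users, which is the ceiling on matched pairs. From 9.2.1: the longest possible follow-up is about 3.5 years (28 September 2015 to 31 March 2019). The plan gives no figure for events after escalation, so there is none to reproduce. Its 141 events for the primary endpoint fit a hazard ratio of 1.73 (Schoenfeld formula: 140) and are not touched by this point.

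**1. Person-time lost.** Assume constant hazards λ = −ln(1−p): −ln(0.94) = 0.0619 for Tio/Olo and −ln(0.90) = 0.1054 for Tio. With no other censoring, the proportion escalated by T is 1 − exp(−λT). The share of person-time after escalation is f = 1 − (1 − exp(−λT))/(λT). At 1 year, Tio/Olo gives 1 − 0.06/0.0619 = 3.0% and Tio gives 1 − 0.10/0.1054 = 5.1%.

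| Follow-up for all (Tio/Olo vs Tio) | Escalated | Person-time lost | Person-years lost, 1,829 per arm |
|---|---|---|---|
| 1 year | 6.0% vs 10.0% | 3.0% vs 5.1% | 55 vs 93 |
| 2 years | 11.6% vs 19.0% | 5.9% vs 9.8% | 217 vs 360 |
| 3.5 years | 19.5% vs 30.8% | 10.1% vs 16.4% | 646 vs 1,048 |

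The last row is an upper bound. Entry runs to 31 December 2018 and proxy disenrolment shortens follow-up further.

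**2. Event counts.** Assume the event rate after escalation is k times the rate before. The share of events lost is kf/((1−f)+kf).

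- At 1 year (Tio/Olo vs Tio): 3.0% vs 5.1% for k=1, 5.9% vs 9.7% for k=2, 8.6% vs 13.9% for k=3.
- At 3.5 years: 10.1% vs 16.4%, 18.3% vs 28.1%, 25.2% vs 37.0%.
- With equal true event rates, the observed Tio to Tio/Olo count ratio would be 0.98 to 0.94 at 1 year and 0.93 to 0.84 at 3.5 years.

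**3. Rates.** If escalation is unrelated to event risk, rates per person-year are unbiased. To see the effect of a link, take inpatient death with no treatment effect. Every input here except 6% and 10% is an assumption: 20% of patients high-risk, death hazards 0.15 and 0.03 per year, and end of data uniform over 0.08 to 3.5 years. High-risk patients escalate m times as often, with the low-risk hazard q solved from 0.8·exp(−q) + 0.2·exp(−mq) = 1 − p in each arm.

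| m | Deaths uncounted, Tio/Olo vs Tio | Null rate ratio, Tio/Olo vs Tio |
|---|---|---|
| 1 | 6.5% vs 10.7% | 1.00 |
| 3 | 9.1% vs 14.7% | 1.02 |
| 6 | 10.9% vs 17.4% | 1.03 |
| 10 | 12.1% vs 19.1% | 1.04 |

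The ratio of raw death counts moves further: (1−0.091)/(1−0.147) = 1.07 for m=3 and (1−0.121)/(1−0.191) = 1.09 for m=10. With follow-up of at most 1.75 years, the rate ratio for m=3 to 10 is 1.01-1.03.

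As a second check, let one gamma frailty (variance 0.5 to 2) drive both escalation and recurrent events. The Tio to Tio/Olo rate ratio is then 0.99 to 0.96 at 1 year, and 0.97 to 0.90 if everyone had 3.5 years, when the truth is 1.0.

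**The case against.** The strongest defence is that this is loose drafting, not a chosen rule. The Censoring paragraph sits under the primary outcome, where naming triple therapy is natural. The Figure 1 note and 9.7.3 say only outcome, which could mean each endpoint's own event. That is a fair reading of those two places. It does not dispose of 9.2.1, which is the general definition and names triple therapy, and no section states the alternative.

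Three stronger readings are tempting, and the documents do not support them.

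- A reader might infer that, if outcome means each endpoint's own event, every exacerbation count is capped at one, so that no reading works. The plan lists time to first and number of exacerbations as separate endpoints. A capped count would be redundant, and counting to death, disenrolment or end of data is an available reading.
- A reader might infer a flat contradiction with intention to treat. Section 9.3.2.1 explains that approach as keeping events in the original group after discontinuation or crossover. Stopping at triple therapy is in tension with it and no more.
- A reader might infer a bias against Tio/Olo. That follows from 6% versus 10%, but Section 9.9 warns that monotherapy patients may take longer to reach triple therapy, which would reverse the direction.

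The objection on size also stands. With 1,829 per arm, the death illustration leaves about 130 to 145 counted deaths per arm. The standard error of the log rate ratio is about √(1/145 + 1/136) = 0.12, so a shift of 1.02-1.04 is 0.16 to 0.35 of one standard error.

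**Conclusion.** The point holds as a defect in the non-primary endpoints that should be fixed before analysis. It does not threaten the primary endpoint or its sample size. As written, the plan discards post-escalation events, probably informatively and unequally between arms.

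The loss is modest at 1 year (3% vs 5% of person-time) and at most about 10% vs 16%. It falls hardest on counts and mortality. For time-to-first endpoints, only patients still event-free at escalation are affected. The distortion of a rate ratio is small in the death illustration (1.02-1.04) and essentially nil if escalation is unrelated to risk. It becomes larger only with a strong shared risk and long follow-up for everyone.

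These sizes rest on constant escalation hazards at the plan's own rates and on the stated risk assumptions. The direction is open. Choosing a window after seeing results would be a post hoc decision, which is a further reason to settle the wording now.

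**What to change.** Define the end of follow-up per endpoint in 9.2.1 (including the Figure 1 note), in the Censoring paragraph of 9.3.2.1 and in 9.7.3, using the same list each time. At present 9.2.1 includes disenrolment and 9.3.2.1 does not.

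- **Primary endpoint:** keep the current 9.2.1 rule.
- **Each time-to-first secondary or further endpoint:** its own first event, inpatient death, disenrolment (the plan's encounter-based proxy) or 31 March 2019, whichever is first.
- **Count endpoints:** inpatient death, disenrolment or 31 March 2019, with person-time as offset.
- **Triple therapy:** state that starting it does not end follow-up for non-primary endpoints in the intention-to-treat analysis, and state explicitly whether it does in the as-treated analysis. Stopping at triple therapy can be kept as a labelled sensitivity analysis.

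The cost is wording in those sections and one derived end date per endpoint, from data already held. The downside is that treatment after escalation becomes part of the secondary comparison, which the intention-to-treat approach already accepts.

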9.2.2 Study population

The study cohort will include all patients who initiate Tiotropium/Olodaterol (Tio/Olo) or Tiotropium (Tio) during the patient selection period. Initiation (new use) will be determined based on no prescription claims for Tio/Olo or Tio during the baseline period or during all available data prior to cohort entry date. All patients will additionally be required to have a second claim for the index medication within 60 days after cohort entry to ensure primary adherence of index therapy.

The following exclusion criteria will then be applied to generate the unmatched cohort:

- Aged <40 years on cohort entry.

[figure not shown]
Proprietary confidential information © 2020 Boehringer Ingelheim International GmbH or one or more of its affiliated companies

- Any LAMA, LABA, ICS maintenance therapy (alone or in combination) during the 180-day baseline period prior to cohort entry for maintenance treatment and not cough, i.e. duration >30 days, or any prescription within the 30 days prior to cohort entry.
- Patients without continuous enrolment (days since first inpatient/outpatient encounter in the data) during the baseline period.
- No prior diagnosis of COPD [ICD-10: J41*, J43*, J44* and doubt (UTAGAIFLG) = 0 (no)]
- Patients without a second prescription claim of their index medication within 60 days after the cohort entry date.
- Diagnosis of asthma [ICD-10: J45* and doubt (UTAGAIFLG) = 0 (no)] during the baseline period.
- Diagnosis of lung cancer [ICD-10: C34*, D02.2, Z80.1, Z85.1 and doubt (UTALAIFLG) = 0 (no)] or lung transplant (Health claim code: 150317670, 150322510, 150322610, 150336510, 150336610, 150336710, 150399270) prior to the cohort entry date using all available data.
- Patients who initiate both Tio/Olo and Tio simultaneously on the cohort entry date.
- Any use of triple therapy (LAMA + LABA + ICS) during the baseline period or between the cohort entry date and 1 day prior to the start of follow-up.

All patients will be selected into the first treatment arm (Tio/Olo or Tio) that they qualify for and will not be allowed to re-enter the cohort by design.

The cohort will then be used to construct two matched cohorts (not mutually exclusive) according to the: 1) basic propensity scores and 2) high dimensional propensity scores

Figure 2 Depicts the flow diagram of patients.

Basic Propensity Score Matching

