9.4 DATA SOURCES

The proposed study will utilize data from Medical Data Vision (MDV).

MDV is an electronic, record-based healthcare database that spans from April 1, 2008 to 31 March 2019, and contains 25.1 million observable patients. It contains patient-level information on demographics, diagnoses and prescription information from 374 medical facilities across Japan. The distribution of patients in the database is similar to that of the national demographics for patients seeking healthcare, although the MDV database has more elderly and sicker patients.

The Japanese health care structure enables anyone to seek medical treatment at any facility of their choosing, including hospitals. Thus, acute hospitals in Japan consist of both primary (outpatient) and secondary (inpatient) care facilities. In fact, the MDV database is built out of more than 80% outpatient data, which allows for identification of patients who visit hospitals without severe conditions. These hospitals follow a diagnosis procedure combination (DPC) billing structure unique to Japan that enables capture of inpatient discharge summary

information (disease name, operations, adjuvant treatment, etc.), health claims for procedures (surgery information, departments, wards, etc.), and health claims for treatments (medications, medical devices, devices, etc.). A smaller subset of consenting hospitals also provide data on blood test results.

Thus, it is expected that 1) patients with COPD in these hospitals provide a good representation of the general Japanese COPD population; and 2) data from patients treated in the different hospitals cannot be linked. Due to the nature of the database, inclusion criteria to ensure that the patients are treated for COPD in the same hospitals continuously are defined as described in [Section 9.2.2](#).

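### As written, continuous enrolment requires no encounter during the 180-day baseline, so a patient not seen in that window passes the washout by default

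*Combined protocol and SAP*

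**What the plan says.** Section 9.2.1 notes that enrolment has no literal meaning in Japan and substitutes a proxy: "start of enrolment = date of first inpatient/outpatient encounter; end of enrolment = date of last inpatient/outpatient encounter will be used". It adds that "patients will be required to have had at least 180 days of enrollment prior to the cohort entry date". Section 9.2.2 turns this into an exclusion: "Patients without continuous enrolment (days since first inpatient/outpatient encounter in the data) during the baseline period".

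The other entry rules in 9.2.2 that bear on prior history are:

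- New use: "no prescription claims for Tio/Olo or Tio during the baseline period or during all available data prior to cohort entry date".
- Washout of LAMA, LABA or ICS over the 180-day baseline: "for maintenance treatment and not cough, i.e. duration >30 days, or any prescription within the 30 days prior to cohort entry".
- COPD, as an exclusion with no time window: "No prior diagnosis of COPD".
- Asthma and triple therapy: excluded if recorded during baseline (triple therapy also between entry and the start of follow-up).

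Section 9.4 states that "data from patients treated in the different hospitals cannot be linked". It then offers a safeguard: "inclusion criteria to ensure that the patients are treated for COPD in the same hospitals continuously are defined as described in" section 9.2.2.

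Two other places describe eligibility differently. The abstract (Population) adds a condition about regular attendance at an MDV facility for COPD, at entry or at any time before it. Section 9.5, and the abstract under Study size, describe the feasibility count as limited to patients with a COPD diagnosis within the baseline period.

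**The concern.** A new-user design needs a baseline in which prior therapy would have been recorded had it been given. Here the rule called continuous enrolment measures elapsed time since a first contact. It does not measure contact during the window that matters. For a patient not seen in that window, no prior inhaler, no asthma and no exacerbation may mean only that nobody was recording.

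Two things are at stake. Some patients counted as initiators may already be on maintenance therapy prescribed at a hospital whose records cannot be linked. The propensity scores may also match on covariates read as negative when they were unobserved. The missing-data indicator in 9.6 would not catch this, because 9.7.1.1 determines comorbidities and medications by whether they occurred in the baseline records, so an absent code reads as a no.

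**Working it through.** The question is what the rules admit, so the check applies them to a patient history and then compares the sections.

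**1. The window itself.** From 1 April 2015 to 28 September 2015 is 29 + 31 + 30 + 31 + 31 + 28 = 180 days, as 9.2.1 states. The length is consistent. The issue is whether anything must be recorded inside it.

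**2. A hypothetical patient.** Entry (day 0) is 1 June 2017. One encounter with a confirmed COPD code is on 27 April 2016 (day -400). There are none on days -180 to -1 (3 December 2016 to 31 May 2017). A second index prescription follows by day 60. The patient is 40 or older, with no lung cancer or transplant recorded. Any inhaler in between came from an unlinked hospital.

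| Rule | Applied to this patient | Result |
|---|---|---|
| 180 days of enrolment (9.2.1, 9.2.2) | Entry minus first encounter = 400 days, at least 180; the last encounter is on or after the second prescription, so the baseline lies inside the span | Passes |
| COPD diagnosis (9.2.2) | Recorded on day -400; no window applies | Passes |
| New use over all available data (9.2.2) | Covers the recording hospital only | Passes |
| LAMA, LABA, ICS washout (9.2.2) | Nothing recorded | Passes by default |
| Asthma in baseline (9.2.2) | Nothing recorded | Passes by default |
| Triple therapy, baseline part (9.2.2) | Nothing recorded | Passes by default |
| Second claim within 60 days (9.2.2) | Tests only time after entry | Passes |

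No rule in 9.2.2 stops this patient, and none sets a maximum gap between encounters.

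**3. The sections side by side.**

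- Section 9.4 relies on 9.2.2 for continuous same-hospital COPD care. Step 2 shows that 9.2.2 has no pre-entry criterion that delivers it.
- The abstract's attendance condition is undefined, does not appear in 9.2.2, and can be met on the entry day or at any earlier time. It does not force a baseline visit.
- The COPD diagnosis within baseline in 9.5 would exclude the patient in step 2. It is therefore a different rule from 9.2.2.

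**4. What the counts describe.** The 1,829 Tio/Olo and 13,132 Tio initiators were counted under the 9.5 rule, so each already has a baseline record. They also stop at 31 October 2018, whereas selection in 9.2.1 runs to 31 December 2018, and they name only the 30-day part of the washout. They are not counts of the 9.2.2 cohort.

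**5. Whether the analyses test it.** None of the five sensitivity analyses in 9.7.3 varies baseline observability. The first relaxes entry to one prescription, and the others change censoring, COPD codes or the handling of asthma.

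**6. Size.** If the cohort is in fact built with the baseline COPD diagnosis of 9.5, no patient lacks a baseline record. If it is built as 9.2.2 reads, the number is unknown. The documents give no share of such patients in either arm and no escalation rate for them, so an effect on the hazard ratio cannot be computed.

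**The case against.** Several points on the other side have weight.

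- **The 9.5 rule would close this gap.** That is true if it is the rule actually programmed. But 9.2.2 is the eligibility list and says otherwise, so the conflict is itself a reason to amend.
- **Covariates are not all absent.** Section 9.3.3 admits records made on the index date, and age, sex, calendar year and hospital size are always known. A reader might infer that an unseen patient has an empty covariate vector, and the documents do not support that. Index-day records still cannot show what was prescribed during baseline, and 9.7.1.1 describes a window that ends before entry.
- **The hdPS includes health service intensity.** Quartiles of total and distinct code counts tend to balance low-contact patients between arms. This reduces the problem but does not recover missing history. The basic propensity score has no such intensity variables.
- **The limitation is partly acknowledged.** Section 9.9 concedes events missed at other centres and maintenance therapy before baseline. It does not concede unrecorded therapy during baseline, and it assumes that all patients are observable throughout the data.
- **A baseline visit would not reveal inhalers prescribed elsewhere.** This stands. One unrelated visit satisfies the condition while treatment at another hospital stays invisible. The condition removes patients with no baseline observation at all and does no more than that.

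**Conclusion.** The point holds as a rule that lacks the property the protocol claims for it. Sections 9.2.1 and 9.2.2 admit patients with no encounter on days -180 to -1, the safeguard cited in 9.4 is not in 9.2.2, and the abstract and 9.5 each state something different. This rests on reading 9.2.2 as the governing list.

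Two stronger conclusions are tempting and not supported:

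- **Arm-specific bias.** A reader might infer that unseen prior use gathers in the Tio arm, because Tio was approved in 2004 and Tio/Olo in September 2015. But a patient on Tio elsewhere can equally enter the Tio/Olo arm as a step-up. Neither the difference by arm nor the direction of bias can be derived, and any contaminated hazard ratio would rest wholly on assumed inputs.
- **A loss that the comparator pool can absorb.** The ratio 13,132 / 1,829 = 7.2 comes from a count that already required a baseline COPD diagnosis. It says nothing about how many patients 9.2.2 as written would lose.

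The number affected is unknown. The correction is cheap and should be made before the cohort is built.

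**What to change.** 1. Reconcile the abstract (Population and Study size), 9.2.2, 9.4 and 9.5 on a single observability rule.
2. In 9.2.2, keep the 180 days since first encounter and add a requirement for at least one recorded inpatient or outpatient encounter at the MDV facility on days -180 to -1. The baseline COPD diagnosis already used for the feasibility count would also achieve this.
3. Report, per arm, how many otherwise eligible patients have no encounter in that window.
4. Repeat the primary hazard ratio with and without those patients.
5. Recount the available patients under the final rule and replace the figures in 9.5.
6. Correct 9.4 to say what 9.2.2 does ensure. State in 9.9 that maintenance therapy prescribed at an unlinked hospital during baseline stays unseen even with this condition.

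The cost is one filter on existing data, one tabulation, and one further matching and Cox run for each matched cohort. The downside is that some patients are lost, possibly including genuinely untreated patients with little hospital contact, who fit the study's early-intervention aim. The loss in the Tio/Olo arm, the smaller arm in the feasibility count, should be reported.
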